There will be a total of three replications of the Automatic Oxygen Control System devices at each site. These three devices will be used under the supervision of a study engineer and/or healthcare provider.

There are no known difficulties in using the device.

The cost of the device is funded by the study.

Doctors, respiratory therapists, and nurses will be trained on how to use the device. They will receive training on how to turn the device off and on, switch between automatic and manual modes, and adjust the FiO2 settings on the device. This training will be conducted by the study personnel prior to placing the device on a patient. This training should take less than 5 minutes to complete. A member of the study personnel will be present at the infant's bedside during the first 12 hours of the study period the infant is attached to the device and then 1 hour daily to make sure the device is functioning properly. A member of the study team will also be on-call during the entire study period to answer questions about the device.

The study device will not be documented in the medical records. The study PI and study engineers will be trained in Medical Device Reporting principles.

The study will only last 144 hours. No follow up visits or tests are required.

This device is considered a non-significant risk device requiring no IDE.

7. Study Statistics

a. Primary outcome variable.

- Mean elapsed time needed to re-establish SpO2 within the desired range after an alarm. Does the computer do a better job of keeping the patient in the desired saturation level range compared to the current manual mode? Does the patient return to the prescribed saturation level range quicker in the automatic mode compared to the manual mode?

b. Secondary outcome variables.

- Proportion of time SpO2 is within the prescribed range computed using an area-under-the-curve approach. Is our device safe to use on neonates? Is the transition from automatic to manual mode smooth? Does the device respond appropriately to the patient's saturation level?
- Does the frequency of acute events (apnea, bradycardia and/or desaturation events) decrease if the oxygen saturation level is kept under better control?

- c. Our goal is to enroll 60 patients into the study. We expect to consent 70 subjects to account for drop-out.

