Cover Page

NCT04269161

NICU Oxygen Control Study

Statistical Analysis Plan

October 21, 2024

Statistical Design and Power

A crossover design was chosen because premature infants should have fewer events as they grow older each day, and a crossover design will mitigate this potential confounding effect. Furthermore, because every subject receives the device and the standard of care (nurse only), every subject serves as their own perfectly matched control. All subject-specific effects cancel out, so there is no concern for covariate imbalance. Finally, selection bias is minimized because all subjects receive all “treatments”. Nonetheless, the concealed allocation will be used with blocked randomization at each site, using sealed envelopes. The subjects will be randomized to group A or B in sets of 8 (i.e. in each group of 8 envelopes, 4 will be group A and 4 will be group B). During the entire study process the infants will receive normal NICU care and the parameters the SpO_2 range will be set by the physician caring for the infant. There are also built in manual overrides for the device, which allow the NICU staff to make changes while the subject is on the device phase of the study. The device will be able to record these changes and the staff will record their manual interventions in the study diary.

We have planned our sample size using a non-inferiority test for a 24 period, 2 treatment cross-over design, based on our primary endpoint, t_Δ . For a given patient, define $t_\Delta = (\text{mean elapsed time needed for device to re-establish } \text{SpO}_2 \text{ after alarm}) - (\text{mean elapsed time needed for nurse to re-establish } \text{SpO}_2 \text{ after alarm})$. The margin of non-inferiority will be chosen as $t_\Delta > -10 \text{ sec}$, so that a device which is no worse than 10 sec, on average than a nurse will be considered non-inferior. Assuming the standard deviation of $t_\Delta = 12$ and the true mean difference is zero under the alternate hypothesis, a sample size of 48 achieves 88% with $\alpha=0.05$. If there is 16% patient drop-out before crossover, so that the final $n=40$, the power drops to 82%. In all analysis, a (paired) t-test will be used. Our secondary endpoint will be analyzed in a similar manner. The secondary endpoint is the proportion of time SpO_2 is within the prescribed range, using an area-under-the-curve approach (with a discrete state) to account for varying time-on-test.

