We will plan for one interim analysis to determine if the trial should be stopped early due to futility (strong evidence of inferiority, where a confidence interval for t_Δ lies entirely to the left of -10 and doesn't intersect -10) or for efficacy (strong evidence of superiority with margin $> +20 \text{ sec}$). This will be carried out when $n=32$ (16 subjects per site) is attained and stopping decisions will be based on O'Brien-Fleming stopping principles. The interim analysis will be carried out by an independent statistician on the University of Missouri's Data Safety and Monitoring Committee, which is also available to monitor the study for adverse events if requested by the IRB. In the event that the patient drop-out is greater than 16% before crossover, then a more complicated estimation procedure will be employed using mixed effects models; otherwise, complete cases will be used.

Assuming that the probability of enrollment for a given NICU patient is 10% (conservative est.), and because there are ≥ 6 new NICU patients/week at each hospital, we expect to enroll 48 patients and collect data in 43 weeks (11 months).

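### Superiority in recovery time is written only as an interim rule with a 20 sec margin; the SAP prespecifies no superiority test for the final analysis, although the protocol asks whether recovery is quicker

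*SAP*

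**What the plan says.** Protocol section 7a names the mean time to re-establish SpO2 after an alarm as the primary outcome and asks: "Does the patient return to the prescribed saturation level range quicker in the automatic mode compared to the manual mode". Section 7d adds the hope of reaching statistical significance on every study metric.

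The SAP (Statistical Design and Power) takes a different starting point: "We have planned our sample size using a non-inferiority test for a 24 period, 2 treatment cross-over design". The margin is set "so that a device which is no worse than 10 sec, on average than a nurse will be considered non-inferior", and planning assumes that "the true mean difference is zero under the alternate hypothesis". The SD of the endpoint is 12. The stated result is that "a sample size of 48 achieves 88% with" alpha 0.05, falling to 82% at n=40. A paired t-test is named for all analyses, without its null value and without saying whether alpha is one- or two-sided.

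The interim paragraph allows one look at n=32. It may stop for futility, or it may stop "or for efficacy (strong evidence of superiority with margin", given as more than +20 sec, on O'Brien-Fleming principles. No numerical boundary is given. The SAP does not mention superiority anywhere else.

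**The concern.** The interim efficacy rule and the sample-size hypothesis are not two looks at one null hypothesis. One concerns a gain of more than 20 sec, the other a loss of no more than 10 sec. Neither is the question in protocol 7a, which is whether the difference favours the device at all.

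A device that is reliably some seconds faster, but by less than 20 sec, would fail the interim rule. At the end of the trial the only written hypothesis it could satisfy is non-inferiority. A superiority statement could still be made, but its null, its level and its place after the non-inferiority test would all be chosen with the data in hand. Protocol section 13 discloses financial interests in the company that licenses the device's intellectual property, so an unplanned claim of that kind would be examined closely.

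**Working it through.** **Inputs.** From the SAP: margin 10 sec, SD 12, true difference 0, n=48 (40 after drop-out), alpha 0.05, interim at n=32, interim margin 20 sec. The gains of 5, 6, 8, 10, 15 and 20 sec tried below are illustrations; the documents name no relevant gain other than the 20 sec margin.

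**1. The SAP's own power (noncentral t).**

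| Formula | n=48 | n=40 |
|---|---|---|
| Stated in the SAP | 88% | 82% |
| Two groups of n/2, SE = 12 × √(4/n), one-sided 0.05 | 88.5% | 82.7% |
| Same, one-sided 0.025 | 80.7% | 72.8% |
| Paired, SE = 12/√n, one-sided 0.05 | over 99.9% | over 99.9% |

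The stated figures fit a two-group standard error at one-sided 0.05. They do not fit the paired test that the SAP names. Both standard errors are therefore carried forward.

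**2. Direction of the endpoint.** The SAP defines it as "mean elapsed time needed for device to re-establish" SpO2 minus the same quantity for the nurse, so a positive value means a slower device. Read literally, +20 is a device more than 20 sec slower, and −10 as the limit of inferiority also runs against the definition. Below, +20 is read as a gain, the only reading that fits the word superiority.

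**3. What the interim rule requires.** Paired SE at n=32: 12/√32 = 2.12 sec. Information fraction: 32/48 = 0.667.

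- Classical O'Brien-Fleming, final constant 2.003: z = 2.003/√0.667 = 2.453; threshold 20 + 2.453 × 2.12 = 25.2 sec.
- O'Brien-Fleming-type spending, one-sided 0.025: z = 2.509; threshold 20 + 2.509 × 2.12 = 25.3 sec.
- The same at one-sided 0.05: z = 2.135; threshold 24.5 sec.

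The chance of crossing at a true gain of 20 sec is 0.7%, 0.6% and 1.6% respectively. At 15 sec it is under 0.001% in all three.

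**4. What a final test against zero could show (two-sided 0.05).**

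| True gain | Paired, n=48 | Paired, n=40 | Two-group SE, n=48 | Two-group SE, n=40 |
|---|---|---|---|---|
| 5 sec | 81% | 73% | 29% | 25% |
| 6 sec | 92% | 87% | 40% | 34% |
| 8 sec | 99.5% | 98% | 62% | 54% |
| 10 sec | over 99.9% | 99.9% | 81% | 73% |

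The paired 95% CI half-width at n=48 is 2.01 × 12/√48 = 3.5 sec. At the protocol's enrolment goal of 60, paired power for 5 sec is 89%. An SD of 24 in the paired formula gives the same standard error as the two-group columns, because 24/√n = 12 × √(4/n).

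**5. Alpha used by the interim rule.** With the spending boundary, the threshold lies 25.3/2.12 = 11.9 SE from zero and (25.3 + 10)/2.12 = 16.6 SE from the non-inferiority limit. On the two-group SE at n=32, 12 × √(4/32) = 4.24, the threshold is 20 + 2.509 × 4.24 = 30.6 sec, which is 30.6/4.24 = 7.2 SE from zero. Either way the probability of a false stop at either null is negligible. Even if the final test paid for an ordinary O'Brien-Fleming look against zero (final z = 1.99), paired power for 5 sec at n=48 would remain 81%.

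**The case against.** A reader might infer that the final analysis tests only non-inferiority and that a gain of 5 to 20 sec could never be claimed. The documents do not support either statement. The SAP attaches non-inferiority to the sample size; for the analysis it names a paired t-test with no null, and the protocol's wording is that of superiority. A final superiority test is unstated, not excluded. The planned analysis also yields a confidence interval, or the data for one, that anyone can compare with zero.

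A stricter criterion for stopping early than for the final conclusion is not in itself an error, so the small stopping probabilities do not alone show a fault. They matter because no other superiority criterion is written.

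Nor is it established that the trial has the precision to show a 5 sec gain. That holds if 12 is the SD of the within-patient difference, as the SAP literally says. On the standard error behind its own 88%, power for 5 sec is 29%.

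These objections limit the claim. They leave standing that the SAP states no final superiority hypothesis, no order of testing and no link between the interim rule and the final alpha.

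**Conclusion.** The concern holds as a gap in prespecification. The primary question in protocol 7a has no matching final test in the SAP, and the one superiority rule that is written would almost never be met for true gains up to 20 sec (at most 1.6% under the boundaries tried).

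What a final test would add depends on the SD. With 12 sec as the paired SD, gains of about 5 sec and above are detectable at n=48. On the two-group standard error, the figure is about 10 sec. In both cases this lies well below what the interim rule can recognise. The interim figures rest on reading +20 as a gain and on an assumed O'Brien-Fleming boundary, since the SAP gives no number. The point should be corrected before analysis; it does not undermine the non-inferiority conclusion itself.

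**What to change.** 1. Define the direction of the endpoint once, and give the 10 sec and 20 sec limits signs that agree with it. Without this, a sentence on superiority would add to the contradiction.
2. State a fixed sequence for the final analysis: first, non-inferiority against the 10 sec margin at the SAP's alpha, with its sidedness given; second, only if that is met, superiority against zero at two-sided 0.05 from the paired analysis.
3. State the interim boundary numerically, and state that the 20 sec rule spends essentially no alpha at either null, so the final tests keep their level.

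Dropping the 20 sec rule alone would not solve the problem, because no superiority test would then remain at any look.

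**Cost.** A few sentences in the SAP and no extra patients. The fixed order needs no division of alpha. One choice has a price: if a single two-sided 95% CI serves both steps, non-inferiority is tested at one-sided 0.025, and on the SAP's own power basis its power becomes about 81% at n=48 and 73% at n=40, against the stated 88% and 82%. Keeping the first step at one-sided 0.05 avoids that loss.

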We took these same devices and attached a computer that can receive information about the infant's oxygen saturation level from the pulse oximeter and can automatically turn the knob on the blender in order to adjust the oxygen level being delivered to the infant to keep the oxygen saturation level in the desired range. The computer also has an artificial intelligence algorithm in it, and it will learn to anticipate the patient's oxygen needs the longer it is attached to a patient. For safety concerns, the device also has a switch that the healthcare provider can use to turn the device to manual mode should the computer system not be able to keep up with the infant's condition.

With this study, we will compare how well the computer adjusts the oxygen concentration to keep the baby's oxygen saturation level in the desired range compared to the healthcare providers that must manually adjust the knob whenever the infant's saturation level falls out of range.

2. Objectives

The primary objective to this study is to determine if the computer can automatically keep the infant's oxygen saturation level in the desired range for a longer period of time compared to

the healthcare providers that must manually adjust the oxygen concentration whenever the infant's oxygen saturation level falls out of range. Other objectives of this study are clinical validation of the oxygen control device and algorithm developed by the researchers at the University of Missouri by testing the transitions from automatic to manual control of the device; demonstrate the dynamic adaptability; and show that the response of the system in the automatic model is stable.

We will also monitor the frequency of acute events (apnea, bradycardia and/or desaturation events) to see if the frequency of these events will decrease when the oxygen saturation level is better controlled.

3. **Background** (N/A please see abstract section)

4. **Study Procedures**

- a. Whenever an infant who has been admitted to the Neonatal Intensive Care Unit (NICU) at one of the study sites is placed on a high flow nasal cannula or bubble CPAP by the primary healthcare team, the study personnel will determine if the infant meets inclusion criteria.
- b. The primary healthcare team caring for the infant will continue to adjust the flow on the high flow nasal cannula or the PEEP on the bubble CPAP per the patient's needs.

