Currently healthcare providers care for 2-3 patients in the NICU. To prevent alarm fatigue in our staff, we chose a wide range for our pulse oximeter alarms parameters to minimize the frequency of alarms. If they are in the middle of caring for another patient and another patient's saturations are only slightly out of range, they may take up to a few minutes to respond especially if the saturation level is high. This computerized system will be able to respond instantaneously whereby decreasing the risk for long-term complications. Currently no one knows for sure what the optimal saturation level range should be for preterm infants to prevent these long-term complications. Once we validate this device, we will be able to choose more narrow saturation levels to see if we can improve the outcomes of our patients.

10. Payment and Remuneration

- a. N/A

11. Costs

- a. There are no costs to the patients for this study. The grant will pay for the tubing needed to connect the high flow nasal cannula set-up or the bubble CPAP set-up to the study device.

12. Multiple Sites

- a. The University of Missouri Women's and Children's Hospital (Columbia, Missouri) is the lead site.
- b. All required approvals will be in place at each site prior to project implementation. The study will utilize a single IRB (sIRB). The Studer Family Children's Hospital at Ascension Health (Ascension Sacred Heart Pensacola) (Pensacola, Florida) will be an additional site for the study and will rely on the MU IRB for review. The MU IRB will be responsible for the oversight of the relying IRB.

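### The interim efficacy stop at 32 infants rests on recovery time alone; time in range, acute events and safety have no role in the decision

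*SAP*

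**What the plan says.** The SAP (Statistical Design and Power, interim analysis paragraph) plans one look at n=32, 16 per site, following O'Brien-Fleming principles. The trial may stop for futility, defined by a confidence interval for t_Δ lying wholly below -10, "or for efficacy (strong evidence of superiority with margin" above +20 sec). No other outcome is named in either limb.

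The outcomes are ranked as follows.

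- **Recovery time** is primary in both documents. The SAP sizes the trial "based on our primary endpoint", t_Δ, and Protocol section 7.a lists "Mean elapsed time needed to re-establish SpO2 within the desired range after an alarm".
- **Time in range** is the stated objective in Protocol section 2: "The primary objective to this study is to determine if the computer can automatically keep the infant's oxygen saturation level in the desired range" for longer than manual adjustment does. As an endpoint it is secondary, in Protocol section 7.b and in the SAP: "The secondary endpoint is the proportion of time SpO_2 is within the prescribed range".
- **Acute events and safety** are questions in Protocol section 7.b: "Does the frequency of acute events (apnea, bradycardia and/or desaturation events) decrease if the oxygen saturation level is kept under better control", and "Is our device safe to use on neonates". The SAP names neither as an endpoint.

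Oversight sits apart from the rule. An independent statistician on the university's monitoring committee runs the interim analysis, and that committee will monitor adverse events if the IRB asks. Protocol section 8.c adds a local board drawn from the investigators and study team.

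**The concern.** t_Δ compares mean recovery times per alarm, so it does not count alarms. A controller that ends each excursion sooner but provokes more of them could improve t_Δ while time in range or desaturation counts fail to improve. The Protocol asks about these separately, yet an efficacy stop needs none of them to be looked at, let alone to agree.

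If the rule fired, the trial would end on one metric. The question in Protocol section 2 and the safety question would be left with less precision than planned. An early stop also offers little in exchange: every infant receives both modes, participation lasts 144 hours and there is no follow-up.

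**Working it through.** **1. The plan's own figure.** Inputs from the SAP: margin 10 sec, SD of t_Δ 12 sec, true difference 0, α = 0.05. A two-sample t-test with n/2 per group and one-sided α = 0.05 gives 88.5% power at n=48 and 82.7% at n=40, against the stated 88% and 82%. One-sided 0.025 gives 80.7% and 72.8% and does not reproduce them. The paired test that the SAP names would give over 99.9% at both sizes. That is a separate matter; here it shows only that the planned difference is zero and that α was probably one-sided.

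**2. What the efficacy stop requires.** Standard error at the look: 12/√32 = 2.12 sec. The SAP gives no boundary value. I assume z = 2.51 (O'Brien-Fleming-type spending, two-sided 5%, information 32/48). The classical O'Brien-Fleming bound is 2.45 at two-sided 5% and 2.09 at one-sided 5%. I take gain as device faster, and read the rule as requiring the confidence bound to clear 20 sec. The observed gain must then be at least 20 + 2.51 × 2.12 = 25.3 sec (24.4 with z = 2.09).

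**3. Chance of stopping.** P = Φ((gain - 20)/(SD/√32) - z).

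| True gain | SD 12, z = 2.51 | SD 12, z = 2.09 | SD 24 (assumed), z = 2.51 |
|---|---|---|---|
| 0 or 10 sec | essentially 0 | essentially 0 | essentially 0 |
| 20 sec | 0.6% | 1.8% | 0.6% |
| 25 sec | 44% | 61% | 9% |
| 28 sec | 90% | 95% | not computed |
| 30 sec | 99% | over 99% | 44% |
| 35 sec | over 99% | over 99% | 85% |

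A looser reading needs only an observed mean above 20 sec. With SD 12 the chance is then 0.9% at a true gain of 15 sec, 50% at 20 and 99% at 25, and still nil at zero.

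**4. What is lost if it fires.**

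- Infants: 1 - 32/48 = 33% fewer than the SAP's target, or 1 - 32/60 = 47% fewer than the 60 in Protocol section 7.c.
- Planned hours per mode: 32 × 72 = 2,304 against 48 × 72 = 3,456.
- Standard errors: √(48/32) = 1.22, so 22% larger than at 48; √(60/32) = 1.37, so 37% larger than at 60.
- Upper 95% bound for a harm seen in no infant, 1 - 0.05^(1/n): 8.9% at 32, 6.1% at 48, 4.9% at 60.
- Time in range: the documents give no SD. As a scale-free illustration, a paired effect with 80% power at 48 (standardised 0.41, two-sided 5%) has about 62% power at 32.

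**5. What stopping saves.** The SAP's accrual is 2 sites × 6 per week × 10% = 1.2 infants per week. The remaining 16 infants take 16/1.2 = about 13 weeks.

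**6. The sign.** The SAP defines t_Δ as device time minus nurse time, so a positive value means a slower device and +20 sec describes a device 20 sec slower than the nurse. The non-inferiority margin (t_Δ > -10) and the futility condition (below -10) have the same problem. All three agree with each other only if t_Δ is nurse minus device.

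**The case against.** Stopping on the primary endpoint is ordinary design, and any efficacy stop leaves less secondary data. That stands. Because section 2 makes time in range the objective, a reader might infer that the rule bypasses the primary endpoint. It does not: both documents make recovery time primary. The gap between objective and endpoint is a separate matter to settle.

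A reader might also infer that an early stop is expected, because Protocol section 9 says of staff that "they may take up to a few minutes to respond especially if the saturation level is high" while the computer reacts at once. The text does not carry that far. It describes a response delay in some situations, when staff are busy with another infant and the saturation is only slightly out of range. The endpoint is a mean over all alarms. Section 6 limits the device to 2% steps every 10 seconds with a reliable signal. The pilot's shorter recovery time was not significant, and its size is not given.

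Nor do the documents suggest that the outcomes will diverge. In the pilot (section 7.d) recovery time and time in range both moved in favour of automatic mode and bradycardia fell, though in only 6 infants over 12 hours. If alarm limits match the prescribed range, time out of range is roughly alarms times mean recovery. With assumed figures, 20% out of range at 60 sec per alarm is 0.20 × 3600/60 = 12 alarms an hour; 24% at 35 sec is 0.24 × 3600/35 = about 25. A 4-point loss alongside a 25 sec gain would need alarms to double. That is possible but should not be presumed.

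Finally, oversight exists: an independent statistician, a committee, a local board and IRB reporting. Nothing says the boundary is binding. All of this lowers the risk, but none of it is tied to the efficacy decision.

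**Conclusion.** The concern holds in a limited form. The efficacy rule uses recovery time alone, and nothing requires time in range, acute events or safety to be reviewed before a stop. The rule is very unlikely to fire at or near the SAP's planning assumption and likely to fire only with a true gain in the high twenties of seconds or more. Those probabilities rest on SD 12, an assumed boundary and the intended direction of t_Δ. The documents support neither an expectation of such a gain nor a prediction that the other outcomes would be adverse.

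What remains is a gap when the rule does fire: a third fewer infants and standard errors 22% larger than at the SAP's 48 (37% larger than at the Protocol's 60) for every other question. This is a cheap improvement to make before the look. It does not threaten the primary comparison.

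**What to change.** Amend the SAP's interim paragraph so that an efficacy stop requires both of the following, and otherwise the trial continues to its planned size:

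1. the recovery-time boundary is crossed, with the boundary value and its sidedness stated;
2. an interim review by the independent statistician and the committee shows that the time-in-range estimate does not favour manual mode, and that acute-event and adverse-event data do not point against automatic mode.

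State beforehand whether the second condition is judged on point estimates or with a tolerance. On point estimates alone, if the modes were truly equal on time in range, that condition would fail about half the time by chance.

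In the same paragraphs, reconcile the definition of t_Δ with the signs of the -10 and +20 sec thresholds, and reconcile the planned size (48 in the SAP, 60 in the Protocol).

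The cost is a few sentences and some further summaries at the same look, from data already being collected. An added condition can only make stopping rarer, so it cannot inflate type I error. The downside is a smaller chance of saving up to 16 planned infants, about 13 weeks of accrual at the SAP's target.
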